### **3.1. Randomization, Stratification, and Minimizing Bias**

The randomization should be performed independently for both clinical centers and should be based on the number of hospital medical records. After screening, only eligible patients will be randomized. If the last digit in the number of the hospital medical record is even, the patient should be allocated to the IPC group, and if odd, to the control group. If the last digit in the number of the hospital medical record is zero, the previous digit should be used. Both clinical centers contain multiple medical departments of different specialties, and the numbering of the medical records is performed sequentially through all departments. It starts at the beginning of the year (for example, the first medical record in 2017 is 1/17) and finishes at the end of the year. Taking into account the large admission rate to all medical departments, there is an extremely low probability that two consistently included patients would have sequential medical records. To reduce the bias of the deliberate non-inclusion of the patients with higher VTE risk in the IPC group all non-eligible subjects should be repeatedly evaluated for exclusion criteria by the Data Monitoring Committee.

After allocation to the group, the patient will be assigned an individual code, containing his index number, initials, and year of birth (for example, 1IV1961). This individual code will be used in all study documentation. The allocation list will be stored by the investigator. The blinded expert who will perform a duplex ultrasound scan (DUS) would not have access to the primary medical record or allocation list; he will use only individual patients code for identification. Also, to achieve blindness, most duplex scans will be performed in a separate room away from the patient's bed. If it will be impossible to transfer a patient to the room, the DUS will be performed at the bed, but the IPC device will be removed before the blinded expert's visit. A schematic diagram of the patient allocations is shown in Figure 2.

**Figure 1.** Scheme of the randomization and blindness.

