### 3. Design

A two-center, prospective, randomized (with independent allocation), open-label clinical trial with a blinded assessor for efficacy outcomes, enrolling patients at extremely high risk for postoperative VTE (Caprini score of 11 and more). The patients should be randomly allocated into two groups (experimental [IPC] group and control group) according to the VTE prophylaxis they received. Both groups will receive anti-embolic stockings and injections of LMWH, and patients in the IPC group additionally will receive IPC. The total duration of prophylaxis should amount of 1 month, and patients will be followed-up for 6 months with regular clinical examination and duplex ultrasound scans. Figure 1 represents the global design of the study.

[figure not shown]

**Figure 1.** The global design of the study.

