#### **Inclusion criteria:**

- Age over 40 years;
- Major surgery required;
- High risk of postoperative VTE;
- Caprini score of 11 or more (at extremely high risk of VTE);
- Informed consent is given.

Age over 40 years is suggested as an inclusion criterion by the Russian National Guidelines on VTE prevention, which recognize these patients as a standard high-risk group if undergoing major surgery.

Major surgery is recognized as any procedure under general or regional anesthesia with the leg motor block with a duration of 45 min and more that are equal to major surgery (>45 min) or laparoscopic surgery (>45 min) in the Caprini model.

Primary risk assessment for postoperative VTE should be made according to the rules of the Russian National Guidelines, and only patients at high-risk (major surgery in patients of 40–60 years old with additional individual risk factors, or major surgery in

patients of 60 and more years old independent of additional risk factors) will be screened for eligibility according to the Caprini score.

The Caprini score should be assessed twice: at the baseline screening before inclusion and before discharge or after death. It will be allowed to include patients with supposed scores of  $\geq 11$  (e.g., supposed cancer, supposed long bed rest, supposed CHF, CVD, etc.), but not less than 9. The final assessment of concomitant diseases as risk factors will be performed by an invited specialist. The maximal Caprini score will be taken into account.

**Exclusion criteria:** acute DVT at baseline; performed IVC plication or implanted IVC filter; regular preoperative anticoagulation; postoperative anticoagulation needed at therapeutic doses; absence of anticoagulation  $>5$  days after surgery; coagulopathy (not related to DIC syndrome); thrombocytopenia; hemorrhagic diathesis; lower limb soft-tissue infection; lower limb skin lesion; ankle-brachial index  $<0.6$ .

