**Sample size calculation.** The prevalence of asymptomatic postoperative vein thrombosis at the top of standard prophylaxis with ECS and LMWH was assumed as 30% based on our previous observations involving patients at high and extremely high risk. Taking into account the fact that pharmaco-mechanical prophylaxis should provide a further 60% VTE risk reduction, the absolute difference of 18% is assumed. Using Fisher's exact test for primary statistic analysis, with a power of 80% and type I error of 0.05, the sample size is estimated as 180 subjects (90+90 in each group). Assuming 10% withdrawal due to the protocol deviations, patient's decision, or incomplete data, the sample size is calculated as 200 subjects. Considering prespecified subgroup analysis for the patients with an early and delayed start of LMWH, we decided to double the sample size to achieve sufficient power for separate analyses of the suggested subgroups. IBM SPSS will be used for data processing.

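### Allocation by record-number parity reveals the arm before eligibility and consent are settled, and it yields a 4:5 split instead of the planned equal arms

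*Combined protocol and SAP*

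**What the plan says.** Section 3 describes the trial as "randomized (with independent allocation), open-label clinical trial with a blinded assessor for efficacy outcomes". Section 3.1 gives the mechanism. The hospital record number decides: "If the last digit in the number of the hospital medical record is even, the patient should be allocated to the IPC group", with odd digits going to control. For zero, "If the last digit in the number of the hospital medical record is zero, the previous digit should be used". Within each centre "the numbering of the medical records is performed sequentially through all departments", restarting every year. No sealed list, envelope or third-party release is described, and the investigator keeps the allocation list.

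The same section recognises a selection risk. "To reduce the bias of the deliberate non-inclusion of the patients with higher VTE risk in the IPC group", it has the Data Monitoring Committee re-examine non-eligible subjects against the exclusion criteria. It also argues that two successive participants are unlikely to have consecutive record numbers.

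Section 3.2 places screening on the day before elective surgery, or just before and up to 12 hours after emergency surgery. Its inclusion criteria require a Caprini score of 11 or more but leave discretion: "It will be allowed to include patients with supposed scores of" 11 or more, provided the score is at least 9.

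The sample size paragraph of Section 8 assumes equal arms: "the sample size is estimated as 180 subjects (90+90 in each group"). This is raised to 200 for withdrawals and then doubled.

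**The concern.** Randomisation protects a comparison only if the person enrolling cannot foresee the next assignment. Here the arm is a fixed function of a number on the patient's own file. The protocol does not say when the number is issued. However, records are numbered sequentially across departments, and screening takes place among patients already admitted, so the number can be expected to exist before eligibility is judged. For emergency cases screened after surgery, the recruiter may also know how the operation went.

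Eligibility is partly a forecast (suspected cancer, expected long bed rest), so a recruiter can, knowingly or not, admit a borderline patient in one arm and pass over a similar one in the other. Neither Fisher's test nor the blinded ultrasound reader corrects this. The first takes the groups as given, and the second protects outcome detection, not the make-up of the arms.

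The treatment of zero raises a second, smaller issue. Five digits lead to control and four to IPC, so the rule cannot deliver the equal arms of Section 8. An undeclared shortfall in the IPC arm could be mistaken for the selective non-inclusion that Section 3.1 fears, or could hide it.

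**Working it through.** **Inputs.** From Section 8: control rate 30%; 60% relative reduction, hence 12% under IPC; two-tailed Fisher's exact test; type I error 0.05; power 80%; 90 per arm; 10% withdrawal; then doubling. From Section 3.1: the digit rule. From Section 1: VTE of 59% at Caprini 11 or more and 3% at 10 or less. Last digits are taken as uniform because numbering is sequential.

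**1. The plan's own figure.** The continuity-corrected two-proportion formula for 30% against 12% gives 90 per arm. Exact enumeration of the Fisher test gives 81.2% power at 90:90. Allowing for withdrawal, 180/0.9 = 200, and doubled this is 400. The stated sample size reproduces, but only with equal arms.

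**2. Share allocated to IPC.** Let P be the probability of IPC. Four of ten last digits (2, 4, 6, 8) give IPC, five give control, and one (0) repeats the question on the preceding digit:

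P = 4/10 + (1/10)P, so P = 4/9 = 44.4%.

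Applying the rule to record numbers 1 to 9,999 gives 4,444 IPC and 5,555 control, exactly 4:5. The protocol does not say what happens when the preceding digit is also zero. If that second zero counts as even, P = 4/10 + (1/10)(5/10) = 45%, or 9:11.

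| Total | Planned | IPC:control at 4/9 | IPC:control at 45% |
|---|---|---|---|
| 180 | 90:90 | 80:100 | 81:99 |
| 400 | 200:200 | 178:222 | 180:220 |

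Under a Binomial(400, 4/9) distribution, the IPC arm reaches 200 with probability 1.5% (2.5% if P = 45%).

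**3. Effect of the ratio on power.** Exact Fisher power for 30% against 12% is 82.8% at 80:100, compared with 81.2% at 90:90. Nothing is lost.

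**4. Effect of selection (illustration).** Suppose IPC does nothing, but the proportion of patients truly scoring 11 or more is lower in the IPC arm by d. The expected rates then differ by d × (59% − 3%) = 0.56d. The values of d are assumptions; the documents give none. The test is the unadjusted two-sided Fisher test with a 30% control rate. The total of 360 is 400 less 10%, shown both as 180:180 and at the rule's own 4:5 split.

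| d (points) | Spurious difference (points) | IPC rate | Rejection, 180:180 | Rejection, 160 IPC:200 control |
|---|---|---|---|---|
| 0 | 0 | 30.0% | 3.8% | 4.3% |
| 5 | 2.8 | 27.2% | 7.2% | 8.0% |
| 10 | 5.6 | 24.4% | 18.9% | 20.0% |
| 15 | 8.4 | 21.6% | 39.9% | 41.3% |

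**5. Coverage of the safeguard.** The Committee re-check concerns people recorded as non-eligible and looks at exclusion criteria, whereas the Caprini threshold is an inclusion criterion. It therefore misses borderline patients who were admitted, patients who declined, and anyone not approached. The remark about consecutive numbers concerns independence between patients; each patient's own number still gives the arm.

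**The case against.** Several points on the other side are fair.

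- **The ratio is minor.** An unequal split unrelated to patient characteristics causes no bias, Fisher's test remains valid and power is not reduced. No ratio is stated in words; 1:1 is inferred from 90+90. This stands, so the weight of the finding rests on concealment.
- **Adjustment is planned.** Section 8 prespecifies Cox models adjusted for centre, surgical factors, malignancy, Caprini score and timing of LMWH, and the illustration in step 4 works entirely through Caprini score. The rejection rates therefore apply only to the unadjusted test. But that test is the primary analysis. Sections 3.2 and 5.2 also indicate that the maximal score counts, with the final score set at discharge or death, so it can include events after allocation. Nor can adjustment reach unmeasured reasons for selection.
- **The illustration is hypothetical.** The imbalances have no source in the documents. The 59% and 3% rates were seen with unfractionated heparin, not enoxaparin. Combining them with a 30% control rate implies that only (30 − 3)/(59 − 3) = 48% of controls truly score 11 or more. The table shows sensitivity and does not predict the bias.
- **Timing and screening.** That the number precedes enrolment is inferred. Section 3.2 also requires all surgical admissions to be screened, so failing to approach a patient would breach the protocol. Refusals and discretionary inclusions remain open.

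None of this supplies the missing concealment.

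**Conclusion.** The concern holds, and the plan needs changing before it is relied on. The serious part is that allocation is predictable from the record number while eligibility involves judgement and the trial is open-label. The protocol recognises the risk but guards against only part of it. The size of any resulting bias cannot be derived from the documents. Under the assumptions in step 4, a 10-point imbalance in truly extreme-risk patients would raise the false-positive rate of the primary test from 3.8% to about 19%, and enrolling more patients would not remove the bias.

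The secondary part is exact apart from one ambiguity. The rule gives IPC a 4/9 share (45% on the other reading of a double zero), not one half. It costs no power, but it contradicts the equal arms of Section 8 and weakens arm counts as a check on selective inclusion.

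The conclusion rests on two assumptions: last digits are close to uniform, and staff who enrol patients can see the record number.

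**What to change.** Replace the digit rule with a computer-generated 1:1 list in permuted blocks of varying size, stratified by centre. Release each assignment, by web, telephone or sealed opaque envelope, only after eligibility, baseline Caprini score, baseline duplex scan and consent are recorded. The list should be held by someone not involved in enrolment.

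If the digit rule has to stay:

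- assign a final zero to IPC, so that five digits lead to each arm;
- describe the trial as quasi-randomised in Section 3;
- restate the expected arm sizes in Section 8;
- report every screened patient by record-number parity, including refusals and reasons for non-inclusion.

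This fallback corrects the ratio and makes selection visible, but it does not provide concealment.

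The cost is a protocol amendment and a prepared list or set of envelopes. No additional patients or study procedures are needed.

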### 5.3. Duplex ultrasound scan

Duplex ultrasound scans will be performed by two blinded experts based at different clinical centers. At Center 1, all investigations will be done with MyLab30 (Esaote, Italy) using a linear transducer with a frequency of 5–13 MHz. At Center 2, Voluson I (General Electric, USA) with a linear transducer frequency of 5–13 MHz will be used. All veins of the calf and thigh should be observed during every DUS.

Examinations should be performed in a horizontal position: the common femoral (CFV), the femoral vein (FV), the great saphenous vein (GSV) and its tributaries should be evaluated in the supine position with light bending in the knee joint. The popliteal vein (PV), small saphenous vein (SSV), and its branches should be examined in the prone position. If it is not possible to move the patient or the patient is unconsciousness, the PV

and SSV may be observed during leg supination and bending in the knee joint by ~45 degrees. The posterior tibial veins (PTV) and the medial group of the calf muscle veins should be examined in the supine position with the supinated and slightly bent in the knee joint leg. The peroneal veins (PeV) and lateral calf muscle veins should be examined in the supine position with pronated and knee bent at 45–90 degrees leg. The anterior tibial veins (ATV) should be investigated in the supine position with an unbent knee. In case of any problems with calf vein visualization, the examination should be repeated in the sitting position with the leg bent in the knee joint at 45 degrees.

The main criterion for vein patency is compressibility in the B-mode. If it is necessary, the color flow mode may be used to reveal blood flow in the target vein with the stimulation by manual compression or active movements in the ankle joint. Iliac veins and IVC should be observed in case of clinical suspicion of their thrombosis using convex transducer with the frequency of 2.5–5 MHz.

During the primary DUS, it is obligatory to document all post-thrombotic vein changes, such as residual venous obstruction and valve insufficiency, and their localization in patients with a personal history of DVT. The re-occlusion of the previously affected vein revealed during DUS follow-up must be considered as a new DVT. However, any changes in the degree of residual venous obstruction should not be considered.

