Besides venous investigation, the ABI at the posterior tibial artery should be measured using the pulsed wave Doppler method in all screened patients.

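### Section 3.1 issues the blinding code only after allocation, so the baseline ultrasound scan has no arm-neutral identifier in a trial where the hospital record number gives the arm

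*Combined protocol and SAP*

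**What the plan says.** All references are to the combined protocol and SAP.

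- **Code (3.1).** "After allocation to the group, the patient will be assigned an individual code, containing his index number, initials, and year of birth".
- **What the expert may see (3.1).** The expert "would not have access to the primary medical record or allocation list; he will use only individual patients code for identification".
- **Allocation (3.1).** Only eligible patients are randomized, after screening. "If the last digit in the number of the hospital medical record is even, the patient should be allocated to the IPC group"; an odd digit means control. "If the last digit in the number of the hospital medical record is zero, the previous digit should be used".
- **Eligibility (3.2).** The exclusions include "acute DVT at baseline" and an ABI below 0.6.
- **Who scans (5.3).** "Duplex ultrasound scans will be performed by two blinded experts based at different clinical centers". The section also requires a primary DUS that documents existing post-thrombotic changes.
- **ABI (5.3).** "Besides venous investigation, the ABI at the posterior tibial artery should be measured", and this applies to everyone screened.
- **Primary endpoint (3.5).** Asymptomatic lower-limb venous thrombosis found by DUS in hospital.

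**The concern.** The blinding procedure depends on a code that does not exist when the first scan would normally be done. In most trials this would be harmless, because a hospital number tells a reader nothing about treatment. Here the parity of its last non-zero digit is the allocation, so anyone who knows the rule and sees the number knows the arm.

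The trial is otherwise open-label, and the primary endpoint rests on one ultrasound reader per center. Masking that reader is the main safeguard against detection bias. Issuing a code later does not necessarily restore the mask. The code contains initials and year of birth, and follow-up readings refer back to earlier findings: re-occlusion of a previously affected vein counts as new DVT (3.5, 5.3), and post-thrombotic changes not documented before count at days 30 and 180 (5.5). A later scan can therefore be linked to the first one.

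This point concerns masking of the outcome reader. Selection of patients at enrolment is a separate matter.

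**Working it through.** **1. Order of events.** The plan gives no figure on this point, so the check sets the sections side by side.

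| Step | Source | What follows |
|---|---|---|
| Eligibility is settled before randomization | 3.1 | Any test used for eligibility precedes allocation |
| Acute DVT and ABI below 0.6 exclude the patient | 3.2 | A leg-vein assessment and an ABI are needed for eligibility |
| ABI is measured in all screened patients | 5.3 | ABI precedes allocation |
| Duplex scans are done by the blinded experts | 5.3 | The expert is the natural person to do the baseline scan |
| The code is issued after allocation | 3.1 | No code exists at that scan |
| The expert identifies patients by code only | 3.1 | The rule cannot be followed for that scan |

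Section 5.4 lets duty staff do emergency scans during inpatient follow-up, subject to the expert's verification. That exception does not cover baseline.

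**2. Does the record number fix the arm?** Yes. Applying the digit rule, including the rule for zero, to record numbers 1 to 9999 places every number in exactly one arm (44.4% IPC, 55.6% control). The number determines the arm with no remaining uncertainty.

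**3. Is the number kept from the reader?** Section 3.1 denies the expert the primary medical record and the allocation list. It does not mention request forms, the scanner's patient-ID field or scan reports. The documents are silent on what these show.

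**4. What could be at stake.** The plan's sample size reproduces: 30% against 12% (18 points), two-sided 0.05 and 80% power give 90 per arm with continuity correction, with exact Fisher power of 81.2%; 180/0.9 = 200. Section 8 then doubles this to 400, or 200 per arm if split equally.

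Inputs from section 8: 30% control rate, two-tailed Fisher test at 0.05, 200 per arm. Assumptions not in the documents: no true effect; a share *s* of IPC patients whose arm the reader knows; and a fraction *b* of thromboses missed in those patients. The observed IPC rate is then

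0.30 × (1 − *s* × *b*).

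For example, *s* = 0.25 and *b* = 0.30 give 0.30 × 0.925 = 27.75%. Exact enumeration of the Fisher test gives these rejection rates:

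| Share exposed *s* | *b* = 10% | *b* = 20% | *b* = 30% |
|---|---|---|---|
| 100% | 8.4% | 23.7% | 49.9% |
| 25% | 4.2% | 5.0% | 6.4% |
| 10% | 4.0% | 4.1% | 4.3% |

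With no bias the rate is 3.9%. The apparent relative risk is 1 − *s* × *b*: 0.90 to 0.70 with full exposure, and 0.975 to 0.925 with a quarter exposed.

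**The case against.** The strongest reply is that two links in the chain are inferred.

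- **The expert scans before allocation.** No section says so. Section 5.1 does not list DUS in the baseline examination, 5.3 names no ABI operator and gives no timing for the primary DUS relative to allocation, and the DUS condition for applying IPC in 4.3 could be met after allocation. The diagrams of the design and of randomization and blinding are not visible in the text reviewed and may show this step. The objection stands in part: the sequence is the natural reading of 3.1, 3.2 and 5.3, but it is not stated.
- **The expert sees the record number.** A reader might infer that every patient is scanned under a hospital identity that reveals the arm. The documents do not support this. Section 3.1 bars access to the medical record, and a name, or initials with year of birth, identifies a patient without showing the digit. This objection stands in full. What remains is that no arm-neutral identifier is specified and that request forms, scanner fields and reports are not covered.

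It is also fair to say that one sight of a number need not unblind all later scans. The reader would have to know the rule, note the parity and recall it at scans every 3–5 days. The protocol adds other safeguards: a separate scanning room for most scans, and removal of the device before bedside ones. Finally, the leak exists only because the record number determines the arm; under concealed random allocation, seeing it would reveal nothing.

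**Conclusion.** The point holds as a gap in the blinding procedure. On the natural reading of 3.1, 3.2 and 5.3, the code-only rule cannot be met for the baseline scan, and nothing else in the text protects the identifier used there. Because the record number fixes the arm, the reader of the primary endpoint could be unblinded if it is shown.

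The documents do not establish that unblinding occurs. Nor do they support a single inflated error rate: the 49.9% figure needs every IPC patient's arm to be known and 30% of their thromboses to be missed. The plan gives neither the share exposed nor the size of any reader bias, so the effect can be shown only as a range, from close to the nominal behavior of the test to serious. The change is worth making because it is cheap and protects the only blinded assessment of the primary endpoint. It does not alter the sample size or the analysis.

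**What to change.** In section 3.1:

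1. Assign an arm-neutral screening code before the first DUS or ABI, with no link to the hospital record number, and carry the same code through follow-up.
2. State that ultrasound requests, the scanner's patient-ID field and scan reports, including those for the baseline scan, carry only this code and never the record number.
3. Have someone other than the ultrasound expert transfer results to the medical record.
4. Add the baseline DUS to section 5.1, with its timing relative to allocation and its operator, and name the ABI operator in 5.3.

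The cost is codes for screen failures who are scanned, including emergency cases, and a step to transfer results. No extra scans or patients are needed. If the parity rule were replaced by concealed random allocation, this particular leak would close, and the early code would then serve mainly to make the code-only rule workable at baseline.
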